8.2.2 Primary analysis of the primary efficacy endpoint

The primary endpoint is the HiSCR₅₀ response at Week 16 and corresponding analyses are based on the RS. The primary efficacy analysis will evaluate the composite estimand in the RS as described in Table 8–1. The composite estimand combines the clinically meaningful improvement from Baseline based on the HiSCR₅₀ response and completion of study treatment through Week 16 without receiving systemic antibiotic rescue medication or discontinuing IMP due to an AE or lack of efficacy.

The following 4 attributes describe the estimand that will be used to define the treatment effect of interest for the primary efficacy analysis:

1. Population=Study participants meeting the protocol-specified inclusion/exclusion criteria.
2. Study participant-level outcome=HiSCR₅₀ at Week 16.
3. Intercurrent event handling=An intercurrent event is defined as receipt of systemic antibiotic rescue medication or discontinuation of study treatment due to an AE or lack of efficacy prior to Week 16. More information is provided in Section 3.9. A composite strategy will be implemented in which a positive clinical outcome is defined as achieving HiSCR₅₀ at Week 16 and not receiving systemic antibiotic rescue medication, and not discontinuing study treatment due to an AE or lack of efficacy through Week 16. Any missing data at Week 16 that are not preceded by an intercurrent event will be imputed using multiple imputation as defined in Section 4.2.1. The rationale for this composite estimand is provided in Section 4.2.3.1.

4. Population-level summary measure=conditional odds ratio comparing bimekizumab to placebo adjusted for stratification factors used in the randomization.

The statistical hypothesis for the HiSCR₅₀ response at Week 16 is that the conditional odds ratio for the HiSCR₅₀ response in the bimekizumab treatment group relative to the placebo group is equal to 1.

The primary analysis will be based on a logistic regression model including a fixed effect for treatment, Hurley stage at Baseline, and Baseline antibiotic use. The odds ratio versus placebo, p-value (from Wald test), and 97.5% CI will be calculated. If one dose regimen is tested at the 0.05 significance level as determined in Section 4.5, then the confidence interval will be 95% instead of 97.5% for that dose with a corresponding $Z_{\alpha/2}$ of 1.96.

The number and percentage of participants who are HiSCR₅₀ responders at Week 16 will be summarized.

By-participant listings of HiSCR responder endpoints will be provided.

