2.3 Study design and conduct

2.3.1 Study description

HS0004 is a Phase 3, randomized, double-blind, placebo-controlled, multicenter, pivotal study evaluating the efficacy and safety of bimekizumab in study participants with moderate to severe HS. Study participants meeting the inclusion criteria who do not meet any exclusion criteria will complete a Screening Period of 14 days to up to 5 weeks; a double-blind, 48-week Treatment Period comprising a 16-week Initial Treatment Period and 32-week Maintenance Treatment Period; and a 20-week Safety Follow-up (SFU) Period following the final injection of investigational medicinal product (IMP) if study participants do not enter a subsequent extension study (HS0005) or withdraw prematurely from treatment.

Study participants will be randomized in a 2:2:2:1 ratio (stratified by Hurley Stage and current antibiotic use) to 1 of 3 dose regimens of bimekizumab or placebo as shown in the schematic (Figure 2-1).

Figure 2-1: Study Schematic

HiSCR₅₀=a 50% reduction in the total abscess and inflammatory nodule count with no increase from Baseline in abscess or draining tunnel count;

IMP=investigational medicinal product; [REDACTED]

*Week 16 = primary endpoint (HiSCR₅₀ bimekizumab versus placebo)

a Study participant should discontinue from the study from Week 32 on if no partial response is achieved (partial response is defined as $\geq 25\%$ improvement in abscess and inflammatory nodule count relative to Baseline [Week 0] lesion values.)

b Study participants achieving an improvement of at least 25 % in abscess and inflammatory nodule count continue in HS0005 (Extension Study).

c 20-week Safety Follow-up (from last IMP injection) for any study participant who discontinues from study prior to Week 48, or who does not continue in HS0005.

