2.4 Determination of sample size

A total of 490 study participants will be randomly assigned in a 2:2:2:1 ratio (stratified by Hurley Stage and current antibiotic use) to the following treatment arms:

- Bimekizumab ██████████ during Initial Treatment Period (Weeks 0-16) and Maintenance Treatment (Weeks 16-48) Period, N=140
- Bimekizumab ██████████ during Initial Treatment Period (Weeks 0-16), and Bimekizumab ██████████ during Maintenance Treatment Period (Weeks 16-48), N=140
- Bimekizumab ██████████ during Initial Treatment (Weeks 0-16) and Maintenance Treatment Periods (Weeks 16-48), N=140
- Placebo during Initial Treatment Period (Weeks 0-16), and Bimekizumab ██████████ during Maintenance Treatment Period (Weeks 16-48), N=70

The analysis of the primary efficacy endpoint and secondary efficacy endpoints are based on a comparison of bimekizumab versus placebo at Week 16, with alpha adjustment strategy as indicated in Section 4.5.

The power to detect a statistically significant difference for each of the endpoints are shown in Table 2-1. Notably, with a 2-sided significance level of 0.025, the sample size of 140:70 provides 73% power for detecting at least a difference of 1.5 (bimekizumab ██████████ vs placebo) for the Worst Skin Pain change from Baseline (CFB) endpoint.

Given the high level of power for each of the primary and key secondary endpoints at the 0.025 significance level for the ██████████ comparison (power \geq 0.89), and per the alpha spending strategy, there is a high likelihood that the ██████████ comparison of Worst Skin Pain CFB vs placebo will be allowed to be tested against the 0.05 level of significance. The power for this latter test is 81%. The sample size is thus ultimately driven by the Worst Skin Pain CFB endpoint.

Furthermore, the randomization ratio of 2:2:2:1 has been chosen to provide study participants with a high probability (6/7 ~ 86%) of being randomized to active study drug.

After randomization for this study was complete, an additional endpoint to assess Worst Skin Pain response was included in the sequential testing procedure. This additional endpoint is based on the threshold for clinically meaningful change and is defined as at least a 3 point decrease from Baseline in HSSDD weekly worst skin pain score at Week 16 among study participants with a score of \geq 3 at Baseline. Note that the power calculations reported in Table 2-1 for this

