endpoint are based on the sample size that was initially driven by the Worst Pain CFB endpoint as described above. With a 2-sided significance level of 0.025, the sample size of 104:52 in the subset of participants reporting Baseline HSSDD worst skin pain score at or beyond the threshold for clinically meaningful change (ie, Baseline HSSDD ≥ 3) provides 53% power for detecting a statistically significant difference between bimekizumab [REDACTED] and placebo in the proportion of Worst Pain responders.

Note that the power at the 0.025 level of significance associated with this endpoint for the comparison between bimekizumab [REDACTED] and placebo is 95%. The [REDACTED] comparison of Worst Skin Pain response vs placebo against the 0.05 level of significance is therefore likely, and the power at this significance level is 65%. Given the strength of the power for the bimekizumab [REDACTED] arm vs placebo across endpoints, it is considered acceptable to have a relatively low power for this final endpoint in the testing sequence for the bimekizumab [REDACTED] treatment arm vs placebo.

Table 2–1: Power calculation assumptions and methods

Endpoint	Power $\alpha = 0.025$, 2-sided		Assumptions		
	[REDACTED]	[REDACTED]	Week 16 Bimekizumab [REDACTED] N=280 ^a	Week 16 Bimekizumab [REDACTED] N=140	Week 16 Placebo N=70
HiSCR ₅₀	0.99	0.90	Proportion responders=0.60	Proportion responders=0.50	Proportion responders=0.25
HiSCR ₇₅	0.99	0.98	Proportion responders=0.45	Proportion responders=0.35	Proportion responders=0.10
Flare	0.99	0.99	Proportion of participants with flare by Week 16=0.09	Proportion of participants with flare by Week 16=0.19	Proportion of participants with flare by Week 16=0.52
DLQI	0.99	0.96	Mean CFB=-5.4; SD=6.8	Mean CFB=-4.8; SD=6.8	Mean CFB=-0.8; SD=6.6
Worst Skin Pain CFB ^b	0.89	0.73	Mean CFB=-2.2; SD=3.2	Mean CFB=-2.0; SD=3.2	Mean CFB=-0.5; SD=3.7
Worst Skin Pain Response ^c	0.95	0.53	Proportion responders=0.53	Proportion responders=0.43	Proportion responders=0.23

CFB=change from Baseline; [REDACTED] SD=standard deviation

Note: Estimates for HS0004 are based on Week 12 data from the HS0001 study.

^a Pooled [REDACTED] at Week 16 from [REDACTED] and [REDACTED] arms

^b Within-participant average of Worst Skin Pain according to 24-hour recall.

^c Assumes N=208, 104, 52 in [REDACTED] and placebo, respectively, to account for Worst Skin Pain score at or above 3 (ie, the threshold for clinically meaningful change from Baseline)

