4 STATISTICAL/ANALYTICAL ISSUES

4.1 Adjustments for covariates

The primary efficacy analyses and selected secondary analyses will be adjusted for the 2 randomization stratification variables:

- Hurley Stage at Baseline (II or III)
- Baseline antibiotic use (Yes or No)

If a participant is stratified in the incorrect stratum (ie, the stratum recorded in the Interactive voice or web Response System differs from the actual stratum the participant belongs to), the actual stratum will be used for the analysis.

The continuous secondary endpoints will also include the Baseline value as a covariate.

The Worst Skin Pain secondary endpoints (change from Baseline continuous endpoint and pain response binary endpoint) will also include analgesic use as a covariate.

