4.5 Multiple comparisons/multiplicity

To control the overall type I error rate at 0.05 for the multiple comparisons in the primary and secondary efficacy endpoints, a closed testing procedure under a parallel gatekeeping framework will be applied (Sun, 2018).

[figure not shown]
Under this framework, each bimekizumab dose of [REDACTED] and [REDACTED] will be compared to placebo in the first instance at a familywise error rate of 0.025 ($\alpha/2$). Simultaneously within each dose, closed testing for the primary and secondary efficacy endpoints will be performed as follows:

1. Step 1: Test HiSCR₅₀ at significance level 0.025.
2. Steps 2 to 6 – If Step 1 is significant at 0.025 then test each secondary endpoint sequentially in the order shown in Figure 4-1, moving to the next step only if significance achieved at 0.025.
3. In the event that Step 6 is significant at 0.025 for a given dose, then Steps 1 to 6 will be repeated for the other dose using a significance level of 0.05.

The secondary efficacy variables supporting the primary efficacy variable are listed below, and will be included in the multiplicity adjustment using the analysis methods specified in Section 8.3:

1. Proportion of study participants who achieve HiSCR₇₅ at Week 16.
 - a. bimekizumab [REDACTED] vs placebo
 - b. bimekizumab [REDACTED] vs placebo
2. Proportion of study participants who experience at least 1 flare by Week 16, with flare defined as a $\geq 25\%$ increase in AN count with an absolute increase in AN count of ≥ 2 relative to Baseline.
 - a. bimekizumab [REDACTED] vs placebo
 - b. bimekizumab [REDACTED] vs placebo
3. Absolute CFB in DLQI Total Score at Week 16.
 - a. bimekizumab [REDACTED] vs placebo
 - b. bimekizumab [REDACTED] vs placebo
4. Absolute CFB in Skin Pain Score at Week 16, as assessed by the “worst skin pain” item (11-point numeric rating scale) in the HSSDD.
 - a. bimekizumab [REDACTED] vs placebo
 - b. bimekizumab [REDACTED] vs placebo
5. Skin pain response at Week 16, based on the threshold for clinically meaningful change (defined as at least a 3 point decrease from Baseline in HSSDD weekly worst skin pain score) at Week 16 among study participants with a score of ≥ 3 at Baseline.
 - a. bimekizumab [REDACTED] vs placebo
 - b. bimekizumab [REDACTED] vs placebo

Figure 4-1: Sequence of testing

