A categorical response variable, HiSCR₇₅ at Week 16 is defined to be equal to 1 if % Δ AN is less than or equal to -75%, and the change from Baseline in the abscess count is zero or negative (ie, non-positive) together with a non-positive change from Baseline in the draining tunnel (fistula/sinus tract) count, and 0 otherwise. This definition is introduced for identifying participants who respond to the treatment (1 = responder, 0 = nonresponder). The definition of percentage improvement from Baseline is given in Section 8.2.1.

For HiSCR₇₅ at Week 16, logistic regression as specified for the primary analysis will be implemented to test for superiority. The same analysis approach as outlined for the primary efficacy endpoint will be applied.

8.3.2 Flare by Week 16

See Section 8.2.1 for the derivation of AN count.

Disease flare by Week 16 is defined as at least a 25% increase in AN count with an absolute increase of ≥ 2 AN relative to Baseline is observed by Week 16. A participant's disease flare status (yes/no) will be determined at each visit.

The number of participants who experience at least 1 disease flare by Week 16 will be analyzed using a logistic regression model including a fixed effect for treatment, Hurley stage at Baseline, and Baseline antibiotic use. The odds ratio versus placebo, p-value (from Wald test), and CI will be calculated. Missing data will be handled as described in Section 4.2.1.2.

8.3.3 Change from Baseline in DLQI Total Score at Week 16

The DLQI is a questionnaire designed for use in adult participants with skin diseases and has been used in patients with HS. This is a validated, quality-of-life questionnaire that covers 6 domains including symptoms and feelings, daily activities, leisure, work and school, personal relationships, and treatment, as assessed over the past week.

The scoring of each answer for the DLQI is as follows:

Table 8–3: Dermatology Life Quality Index

DLQI Scoring	
Response	Score
Very much	3
A lot	2
A little	1
Not at all	0
Not relevant	0
Question unanswered	0
Q7: ‘prevented work or studying’ = yes	3

The DLQI total score is calculated by adding the score of each question. The maximum score is 30, and the minimum score is 0. The higher the score, the more quality of life is impaired.

Meaning of DLQI Total Score

0-1 = no effect at all on patient’s life

2-5 = small effect on patient’s life

6-10 = moderate effect on patient’s life

11-20 = very large effect on patient’s life

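### The HiSCR50, HiSCR75 and flare models are valid but omit baseline AN count; adding it would be a cheap, modest gain in power

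*SAP*

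**What the plan says.** Section 8.2.2 fits HiSCR50 at Week 16 by logistic regression with "a fixed effect for treatment, Hurley stage at Baseline, and Baseline antibiotic use". Section 8.3.1 applies the same model to HiSCR75, and Section 8.3.2 lists the same three terms for flare. Attribute 4 of the primary estimand is an odds ratio conditional on the randomization factors only.

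Section 4.1 treats the continuous endpoints differently: "The continuous secondary endpoints will also include the Baseline value as a covariate".

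All three lesion endpoints are defined against baseline AN count. Section 8.2.1 divides the change in AN by it. Section 8.3.2 defines flare as "at least a 25% increase in AN count with an absolute increase of" 2 or more relative to Baseline. Section 4.2.2.1 includes each lesion count at Baseline in the imputation model for that count.

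Participants are "randomized in a 2:2:2:1 ratio (stratified by Hurley Stage and current antibiotic use"), so AN count is not balanced by design. In Section 4.5 the first step for each dose is to "Test HiSCR₅₀ at significance level 0.025", and a dose moves down the sequence only after success.

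**The concern.** A threshold on change from a baseline count invites adjustment for that count, as the plan already does for DLQI and worst skin pain change.

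There is also a mechanical reason to expect some association, because counts are integers and the change actually required varies with the starting value:

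- **Flare:** the two-lesion rule binds up to AN = 8, since 25% of 8 is 2. The rise needed is 2/4 = 50% at AN = 4, 2/5 = 40% at AN = 5 and 2/8 = 25% at AN = 8.
- **HiSCR75:** the reduction needed is 6/8 = 75% at AN = 8, 6/7 = 86% at AN = 7 and 4/5 = 80% at AN = 5.

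Hurley Stage (II or III) can represent lesion burden only coarsely. At stake is a little power on the primary endpoint and on the next two steps of the sequence, together with protection against a chance imbalance in baseline count when the comparator has only 70 participants. The exposed test is HiSCR50 for the single-arm comparison, planned at 0.90: about one trial in ten would stop there at the 0.025 level.

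**Working it through.** **Inputs from the SAP.**

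- Two-sided 0.025 and 140:70: Section 2.4, "with a 2-sided significance level of 0.025, the sample size of 140:70 provides 73% power" (the 73% belongs to worst skin pain change; only the level and sizes are used here).
- Comparator size: Table 2–1, "Week 16 Placebo N=70".
- HiSCR50, single arm: "Proportion responders=0.50"; placebo 0.25.
- HiSCR75: 0.35 and 0.10. Flare: 0.19 and 0.52.

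**Input not in the SAP.** The prognostic strength of baseline AN count is assumed, as an odds ratio per SD from 1.0 to 3.0.

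**Step 1: reproduce the plan's power.** Power = Φ[(|p1 − p0| − z·s0)/s1], with z = 2.241, s0 = √{p̄(1 − p̄)(1/140 + 1/70)} and s1 = √{p1(1 − p1)/140 + p0(1 − p0)/70}.

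| Endpoint | p̄ | s0 | s1 | Power | SAP |
|---|---|---|---|---|---|
| HiSCR50 | 0.4167 | 0.0722 | 0.0668 | 0.907 | 0.90 |
| HiSCR75 | 0.2667 | 0.0647 | 0.0540 | 0.974 | 0.98 |
| Flare | 0.3000 | 0.0671 | 0.0683 | 0.996 | 0.99 |

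The plan's figures are reproduced to within a point. For the pooled 280:70 comparison the same formula gives 0.9996, 1.000 and 1.000 against a stated 0.99, so nothing is to be gained there.

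**Step 2: add a covariate.** 4000 simulated trials of 140:70 per scenario, logistic outcome, intercepts set so that the marginal rates stay at the Table 2–1 values, Wald test at 0.025. The models compared are treatment alone and treatment plus a standardised covariate.

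| OR per SD | HiSCR50 power without → with | HiSCR75 power without → with | HiSCR50 SE of log OR, with covariate | HiSCR50 conditional OR |
|---|---|---|---|---|
| 1.0 | 0.909 → 0.908 | 0.972 → 0.972 | 0.327 | 3.00 |
| 1.2 | 0.895 → 0.897 | 0.971 → 0.972 | 0.327 | 3.03 |
| 1.5 | 0.908 → 0.915 | 0.972 → 0.975 | 0.333 | 3.12 |
| 2.0 | 0.902 → 0.932 | 0.974 → 0.982 | 0.344 | 3.35 |
| 3.0 | 0.903 → 0.952 | 0.973 → 0.986 | 0.370 | 3.87 |

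Without the covariate the SE is about 0.326. Flare power stays at 0.995 to 0.999 throughout.

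**Step 3: does Hurley Stage already capture this?** The HiSCR50 simulation was repeated with a binary Hurley-type factor in both models, at a latent correlation with the covariate of 0.3 or 0.5.

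| OR per SD | Correlation 0.3 | Correlation 0.5 |
|---|---|---|
| 1.0 | 0.906 → 0.905 | 0.911 → 0.907 |
| 1.3 | 0.904 → 0.907 | 0.910 → 0.913 |
| 1.5 | 0.903 → 0.915 | 0.904 → 0.911 |
| 2.0 | 0.904 → 0.929 | 0.900 → 0.925 |

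The gain persists.

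**Step 4: simulation error.** Each power has a standard error of √(0.9 × 0.1/4000) ≈ 0.5 point. Within a scenario the two models see the same trials, so the difference is better determined. At OR 2.0 and correlation 0.3 the adjusted model won 139 trials and lost 37. The net gain is 102/4000 = 2.6 points, with standard error √(139 + 37)/4000 ≈ 0.3 point. The differences at 1.3 or below are too small to count as a gain.

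**The case against.** The strongest reply is that nothing here is wrong. The model carries both randomization factors, matches the estimand's summary measure and agrees with the CMH sensitivity analysis in Section 8.2.3.10. Type I error is untouched. All of that stands.

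A reader might go further than the documents allow in four ways.

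- **That the plan contradicts itself.** It does not. Skin pain response (Section 8.3.5.1) is also a threshold on change, and its model has no baseline score either. The rule is uniform: continuous endpoints adjust for baseline, binary ones do not. Using baseline counts to impute later counts does not oblige the responder model to use them.
- **That precision is being lost.** The standard error of the log odds ratio rises with the covariate. Power rises only because the conditional odds ratio moves further from 1.
- **That the change is free.** The odds ratio is non-collapsible, so a further covariate changes the quantity estimated and its definition must be rewritten.
- **That every participant has a baseline count.** The FAS definition (Section 3.5.4) and the censoring rules in Sections 8.4.1.2 and 8.4.4 allow for its absence, and the primary analysis is on the Randomized Set.

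It is also fair to say that HiSCR is already scaled to baseline and depends on abscess and tunnel counts and on intercurrent events, so the association may be weak. The integer effects show why one is plausible, not how large it is, nor that a single log-linear term fits.

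**Conclusion.** The point holds as an efficiency improvement to a valid model. For HiSCR50 at 140:70 the expected gain is about 0 points for a weak covariate, about 1 point at an odds ratio of 1.5 per SD and about 3 points at 2.0; it reaches 5 points only at 3.0, and in the simulation without a Hurley factor. HiSCR75 gains at most about 1 point and flare essentially nothing, so for those two the case rests mainly on protection against chance imbalance with the 70-participant placebo arm. If the count carries no information, the loss is at most about 0.4 points, which is within simulation error.

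These sizes assume the Table 2–1 rates, a standard normal covariate acting linearly on the logit, and a prognostic strength that the SAP does not state. They do not show that the trial is underpowered or that the planned test is biased.

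**What to change.** Before unblinding, add baseline AN count as a continuous covariate (for example log-transformed, with the form fixed in advance) to the logistic models in Sections 8.2.2, 8.3.1 and 8.3.2, and list it in Section 4.1. Reword attribute 4 in Section 8.2.2 as the odds ratio conditional on the stratification factors and baseline AN count. State that a participant without a baseline count is handled as for deriving the endpoint; since HiSCR and flare cannot be derived from observed data without one, this adds little new missingness.

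The cost is one model term, a reworded estimand attribute and an odds ratio on a slightly different scale (3.12 instead of 3.00 at an assumed 1.5 per SD, 3.35 at 2.0).

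If the sponsor prefers to keep the primary model, a lesser step is to say in Section 4.1 why binary endpoints are not adjusted for baseline and to add the adjusted model to Section 8.2.3, where no listed analysis now includes the count.

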8.2.3 Sensitivity analyses of the primary efficacy endpoint

The following sensitivity analyses for the primary efficacy endpoint will be performed to evaluate the assumptions related to the handling of missing data. Details of the estimands for each analysis are described in Table 8-1.

8.2.3.1 Nonresponse imputation

As a sensitivity analysis, any missing data at Week 16 that are not preceded by an intercurrent event (ie, receipt of systemic antibiotic rescue medication or discontinuation of study treatment due to an AE or lack of efficacy) will be imputed as nonresponse. That is, participants who experience an intercurrent event will be imputed as nonresponder at the timepoint of the event and all subsequent timepoints (including any recorded data after the event), and all missing data will also be imputed as nonresponse.

The same analysis model as in the primary efficacy analyses will then be used on the imputed data set.

